5.4 Follow-up

Patients are in the study for a period of 12 weeks. Thereafter, the patient will be followed up as they would be in normal clinical practice. Study visits are aligned to hospital/clinic visits where possible. Baseline data can be collected on the day of surgery (prior the actual operation), and 12 day and 12 week post-surgery data can be collected when the patient attends for standard follow-up in the orthopaedics out-patient department. The data at day 3, 5, day 12 and week 3 falls outside these dates. For all outcome measures, data can be collected over the phone, via e-mail or by mail (whichever is preferred by the patient – mail is by use of freepost, to avoid patients incurring any costs). The researcher can also send reminders to the participant regarding the completion of certain outcome data at the aforementioned follow-up time points.

5.5 Outcome measures

5.5.1 **Primary outcome measures**

To determine the level of operation-site related pain experienced at day 5 post-operation and to compare the average pain scores of patients in the control and Andoflex TLC Calamine Lite arm respectively, through administration of 10 cm visual descriptor scale (VDS) for pain.

The study is powered to detect the established minimal clinically important difference (MCID) of 1.5 cm on a 10 cm VDS pain.

5.5.2 **Secondary outcome measures**

All the outcome measures are summarised in Table 3.

Table 3. Overview of measurements

Weeks	-12 weeks to day of surgery	0 surgery	3 days ^{##}	5 days ^{##}	12 days [#]	6 weeks*	12 weeks *
Application bandage		Х					
straight after surgery							
VDS pain scale (at rest)	Χ		Χ	Χ	Χ	Χ	
VDS pain scale (walking)	Х		Χ	Χ	Χ	X	
McGill pain	Х		Χ	Χ	Χ	X	
questionnaire							
Limb range of motion	Х					X	
KOOS score	Х					X	Χ
Patient satisfaction					Χ	(X, if not	
questionnaire re						returned	
bandaging						yet at 12	
						days)	

^{*} Allowed to be up to 2 weeks early or late # Allowed to be up to 3 days early or late ## Allowed to be up to 1 day early or late

6. SUBJECTS

6.1 Anticipated number of research subjects

The sample size calculation does take into account a 20% patient attrition rate (withdrawal and loss to follow-up), since this involves a study with multiple time points for data collection up to 12 weeks. Patients will be recruited from the adult (age 18+) population routinely seen by the evaluating clinical staff members. The primary outcome measure is based on knee/leg (ie wound site) pain experienced 5-days post-surgery based on the VDS pain scale 'at rest'. The hypothetical difference in pain perception is 1.5 on a 10 cm scale which equates to a significant 'minimally clinically important difference' for pain (Kelly 2001; Lee et al 2003; Tashjian et al 2009). The values and differences observed in the ROBOT trial will be used for reference.

The non-parametric two-sided Mann-Whitney u-test is applied because the data is ordinal; 80% power and 5% significance is also applied. A priori power calculations using GPower 3.1 software, result in the following sample size summarized in Table 3.

Analysis will be performed on an intention-to-treat basis, although the number of days that a participant has worn a bandage will be recorded.

Data will be analysed as one cohort and also stratified by surgery type (knee replacement, osteotomy) in the resulting analysis.

Table 4, Sample size calculation

	Mean pain score at 5 days post-op	Standard Deviation
Arm A (hypothetical)	5.0	2

Arm B (hypothetical)	3.5	2			
	Power beta of 80%, Alpha p-value of 0.05, Effect size 0.75 Sample size required without any drop-out: 62 samples.				
	Sample size with 20% attrition rate included: 74				
	Total of 74 patients per surgery type:				
	- 37 Patients to receive non-compression bandaging				
	 37 Patient to receive Andoflex TLC Calamine Lite dual-layer compression bandaging 				
	Therefore total is: - 74 knee replacement cases - 74 osteotomy cases				
	Overall trial sample size: 148				

The CONSORT guidelines require a statement on the number of patients assessed for eligibility (Schulz, Altman & Moher 2010). The number of patients screened but who did not meet the inclusion criteria or who declined to participate will be recorded, as will any patients who are lost to follow-up (Appendix 3).

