CASK trial

Compression After Surgery of the Knee trial

CASK trial, A single-centre, two-arm, controlled, prospective randomized trial comparing standard crepe bandaging with Andoflex TLC Calamine Lite (25-30 mmHg) compression bandaging after knee surgery.

Version 1.1, dd 31 August 2021

Chief Investigator's Statement of Ownership and Content.

I, [name], confirm that this protocol is my work and is owned by me. The protocol conforms with standards outlined in the Declaration of Helsinki 1964.

Name (PRINT):_______
Signature:_____

Date: _____

RESEARCH PROTOCOL SUMMARY

TITLE:	CASK trial, A single-centre, two-arm, controlled, prospective randomized trial comparing standard crepe bandaging with					
	Andoflex TLC Calamine Lite (25-30 mmHg) compression					
Characteria	bandaging after knee surgery.					
Short title:	CASK trial; Compression After Surgery of the Knee trial					
IRAS number	288969					
Device description	AndoFlex TLC Calamine Lite Two-Layer Compression System.					
	Compression of 25-30 mmHg. Layer 1 is a soft foam roll					
	impregnated with calamine that is designed to soothe and					
	calm skin. Layer 2 is a non-latex short stretch compression					
	bandage that sticks to itself and features Easy HandTear					
	Technology, eliminating the need for scissors. It provides a					
	two-step short stretch performance with high working					
	pressure and low resting pressure. Visual indicators are					
	provided for ease of application - ovals become circles when					
	the intended compression is achieved.					
Study type	Medical device trial, involving CE-marked devices used for					
	intended purpose.					
Study design	Single-centre, two-arm, controlled, prospective randomized					
	trial.					
Patient population	Adult participants who have knee surgery – specifically knee replacement or osteotomy - and who meet the study inclusion criteria (including being medically fit to have compression bandaging). Participants must have the capacity to provide informed written consent and complete patient reported outcome measures.					
	The study has the following sample parameters: standard deviation of 2 cm per cohort, power beta of 80%, alpha p-value of 0.05. Sample size takes into account 20% attrition rate, effect size of 0.75 (mean difference of 1.5cm on 10cm visual analogue scale) based on previous ROBOT trial results. Total of 74 patients per surgery type:					

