4.2 Secondary objective

- To assess the type of pain experienced by patients wearing either Andoflex TLC Calamine Lite compression bandaging or crepe bandaging.
- To assess the efficacy of Andoflex TLC Calamine Lite compression bandaging for improvement of post-operative patient-reported outcome measures, including knee functionality, after knee surgery when compared with standard care bandaging.
- To determine if there is a difference in pain outcomes dependent on the knee surgery subcohort (knee replacement, osteotomy).

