8.3 Secondary outcome statistics

The average baseline demographics for participants in each group will be compared to ascertain that randomisation has indeed led to comparable distribution of participants:

Sex, age, height, weight, BMI, length of stay, type of anaesthetic for surgery and type of analgesics post-surgery.

To compare outcomes between the two groups (standard vs Andoflex TLC Calamine Lite bandaging), student t-test, Mann-Whitney U-test or Chi-squared test will be applied as applicable, depending on type and distribution of data .

Cox proportional hazards regression analysis will be conducted to investigate the role of bandaging and other covariates (as mentioned above) in post-surgery related pain and knee function.

The statistics apply to:

Up to 12 weeks prior to surgery, and 12 weeks post-surgery, knee function and quality of life measurements: Knee and Osteoarthritis Outcome Score (KOOS), and range of movement of the affected limb (goniometer)

Descriptive safety overview at 30 days and 12 weeks post-surgery:

- Readmitted to theatre and/or hospital
- Infection of wound site
- Diagnosed with pulmonary embolism or deep vein thrombosis
- All monitored remotely by review of patients' hospital notes.

Patient satisfaction survey at 12 days post-surgery – any difference in outcome will be determined with Mann-Whitney U-test

For all outcome measures and statistics, both whole cohort and surgery-specific stratification analysis will be conducted.

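### The protocol does not fix which day-5 pain comparison is primary (whole cohort, knee replacement or osteotomy), and its surgery-type objective has only separate within-type tests

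*Protocol*

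**What the plan says.** Section 4.1 gives one primary objective: less post-operative pain with compression than with standard bandaging after knee surgery, with no split by procedure. Sections 5.5.1 and 8.2 likewise describe one comparison of two arms. Section 8.2 names the Mann-Whitney test but not the population it is run in.

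The sizing in section 6.1 is per procedure. The test is described as "The non-parametric two-sided Mann-Whitney u-test is applied because the data is ordinal; 80% power and 5% significance is also applied", and Table 4 gives "Power beta of 80%, Alpha p-value of 0.05, Effect size 0.75", which leads to 62 evaluable patients. With attrition this becomes "Total of 74 patients per surgery type", doubled to 148.

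Two analysis instructions follow. Section 6.1: "Data will be analysed as one cohort and also stratified by surgery type (knee replacement, osteotomy) in the resulting analysis". Section 8.3: "For all outcome measures and statistics, both whole cohort and surgery-specific stratification analysis will be conducted". Neither gives an order of testing, an allocation of the 5% level, or a statement of which analysis decides the trial.

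Section 4.2 adds a secondary objective: "To determine if there is a difference in pain outcomes dependent on the knee surgery subcohort (knee replacement, osteotomy". No between-type comparison of the bandage effect is specified for it. The regression in section 8.3 refers back to a covariate list in which surgery type does not appear. Section 6.1.1 says that randomisation is carried out separately for each surgery type.

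**The concern.** The objective, the sizing and the analysis instructions point to different confirmatory tests. The objective suggests one test in everyone. The sizing suggests two trials side by side, each with 80% power at 5%. The analysis text prescribes all three comparisons without ranking them. Readers of the results could not tell from the protocol whether a positive osteotomy result with a null whole-cohort result counts as success, and the choice could be made after the data are seen.

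The surgery-type objective raises a related problem. Testing the arms separately within each type does not test whether the bandage effect differs between types. If the two tests fall on opposite sides of 5%, that pattern is easily taken as evidence of a difference when chance explains it.

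**Working it through.** **Inputs.** Difference 1.5 cm, SD 2 cm, d = 0.75, two-sided 5%, 80% power, 62 evaluable per type (31 per arm), 74 per type after attrition (Protocol summary and section 6.1, Table 4). Randomisation per type (section 6.1.1). Day-5 interquartile ranges from the earlier osteotomy trial: 2.5–7.0 and 1.5–6.5 (section 2, Table 1).

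**Step 1: reproduce the stated size.** Take the Mann-Whitney efficiency under normality, 3/π = 0.955, with a noncentral t calculation. At 31 per arm the effective n is 31 × 0.955 = 29.6, the noncentrality is 0.75 × √(29.6/2) = 2.89, and power is 0.810. At 30 per arm power is 0.796. So 31 per arm, or 62, reproduces exactly, as the size for a test inside one surgery type. The step to 74 is 62 × 1.2 = 74.4.

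**Step 2: false positives if any of the three tests could carry the claim.** Under no effect, let Z₁ and Z₂ be independent statistics for the two types, with pooled statistic (Z₁ + Z₂)/√2 for equal-sized types.
- Two types only: 1 − 0.95² = 0.0975.
- All three, allowing for their correlation (simulation, 8 million pairs, critical value 1.96): 0.115.
- All three, favourable direction only: 0.058, against a nominal 0.025.
- Whole cohort designated as the only primary test: 0.05.

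**Step 3: disagreement of the within-type tests.** If the true effect is 1.5 cm in both types, each test has power 0.81. The chance that exactly one is significant is 2 × 0.81 × 0.19 = 0.31.

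**Step 4: power of a direct test of a difference in effect.** With 31 per arm per type, the standard error of the difference between the two effects is SD × √(4/31).
- SD 2: SE = 0.718; 1.5/0.718 − 1.96 = 0.13; power 0.55 (0.53 with Mann-Whitney efficiency).
- SD 3.5: SE = 1.257; 1.5/1.257 − 1.96 = −0.77; power 0.22.

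The 3.5 is an assumption, not a protocol figure. Dividing the Table 1 interquartile widths by 1.349 gives 4.5/1.349 = 3.3 and 5.0/1.349 = 3.7. This treats pain scores as normal, uses 18 patients per arm from an osteotomy trial of a different bandage, and carries the result over to knee replacement.

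**Step 5: power of a whole-cohort test.** With 62 evaluable per arm over both types, d = 0.75 and the same method, power is 0.98. If 20% of the 74 per arm are lost, 59.2 remain and power is still 0.977.

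**The case against.** The best answer is that the protocol already implies a ranking. The primary objective is about knee surgery in general, the surgery-type question is listed as secondary, section 6.1 mentions the single cohort first, and the sentence in 8.3 stands under secondary outcomes. On that reading the primary error rate is 5%. The reading is natural, but the protocol never states it, and the sample size, which is the only place where power and significance are fixed, is worked out for each type alone. It therefore cannot be taken as settled.

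A second defence is that two separately randomised and separately sized populations may each be tested at 5%, and whether such strata must share one error rate is debated. That is arguable. But it is a different design from the one the primary objective describes, and it too would have to be declared.

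A reader might infer that the trial's false-positive rate is simply more than double 5%. The documents do not support that. The 5% level appears only in the sample-size material, its use for each of the three tests is inferred from the absence of any adjustment, and nothing says that one positive test suffices. A reader might also infer that the trial will report a benefit in one surgery type only. No passage commits to that conclusion. The wording of 4.2 could even mean a plain difference in pain levels between procedures, although no between-type test is specified for that either.

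An interaction term for a secondary objective could be left to an analysis plan that is not shown. What the protocol itself fixes is an objective about a difference between types alongside within-type analyses only.

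**Conclusion.** The point holds as an unresolved choice of primary comparison, not as a demonstrated inflation of error. The possible false-positive chance runs from 5% (whole cohort alone primary) through 9.75% (either surgery type) to about 11.5% (any of the three). The higher figures require each test to be at two-sided 5% and any one to be sufficient.

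For the surgery-type objective, read as a difference in bandage effect, the within-type tests are not an adequate answer. They disagree about 31% of the time under an equal 1.5 cm effect at SD 2. A direct contrast is the right tool, but at 0.55 power (0.22 if the SD were 3.5) it would rarely settle the question, so it should be labelled exploratory.

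**What to change.** In sections 6.1 and 8.2, name the whole-cohort comparison of day-5 at-rest pain as the single primary test at two-sided 5%, stratified by surgery type to match the randomisation. A stratified Mann-Whitney (van Elteren) test stays closest to the stated method. A linear model with surgery type as a covariate is an alternative if the change of test is stated, because a plain Mann-Whitney test can neither be adjusted nor hold an interaction term.

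In 6.1, restate that 74 per type serves the precision of the within-type estimates, and that the whole-cohort test has about 98% power under Table 4's assumptions with 62 evaluable per arm. Report the surgery-type results as estimates with confidence intervals. Address the 4.2 objective with a separate arm-by-surgery-type contrast or interaction, labelled exploratory. Make these changes before the interim look at 50% of the data described in section 9.

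The cost is a small revision of the primary test and the sizing text, with no added patients. The real concession is that a finding confined to one surgery type is no longer confirmatory. If the sponsor wants confirmatory claims by type, the alternative is two co-primary tests at 2.5% each. That needs 37 evaluable per arm per type, or 74 evaluable per type, which is 74/0.8 = 92.5, so 93 recruited. With the present 31 evaluable per arm, power would be 0.72.

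### 74 patients per surgery type does not cover the stated 20% attrition: it leaves 59 evaluable, not the 62 the plan requires

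*Protocol*

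**What the plan says.** Section 6.1 defines attrition as withdrawal plus loss to follow-up, sets it at 20%, and explains the figure by the several data-collection points up to 12 weeks. The test and error rates are given as: "The non-parametric two-sided Mann-Whitney u-test is applied because the data is ordinal; 80% power and 5% significance is also applied". The calculation was done in GPower 3.1.

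Table 4 assumes mean day-5 pain of 5.0 and 3.5 with a standard deviation of 2 in each arm, summarised as "Power beta of 80%, Alpha p-value of 0.05, Effect size 0.75". It then gives two totals:

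- "Sample size required without any drop-out: 62 samples"
- "Sample size with 20% attrition rate included: 74"

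The table applies the 74 to each surgery type, as 37 per arm. That makes 74 knee replacements plus 74 osteotomies, 148 overall. The protocol summary repeats these numbers with the assurance "Sample size takes into account 20% attrition rate". The formula used to inflate 62 to 74 is not given.

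**The concern.** Attrition is a share of the patients who enter the trial, so the number recruited must satisfy N × (1 − 0.20) ≥ 62. Adding 20% to the evaluable number is a different operation and always falls short. The figure of 74 looks like the result of that second operation.

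At stake is whether the plan's three linked statements can all be true for a surgery type: 74 recruited, 20% lost, 80% power. Table 4 sizes the trial by surgery type, section 6.1.1 randomises by surgery type, section 4.2 makes a difference in pain by surgery type a secondary objective, and section 8.3 promises surgery-specific analysis of every outcome. The per-type figure is therefore a claim the protocol makes. Any error in it carries into each statement of 37, 74 and 148.

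**Working it through.** **Inputs.** All are from the protocol summary or section 6.1 and its Table 4: difference 1.5 cm; SD 2 cm per arm; effect size d = 1.5 / 2 = 0.75; two-sided Mann-Whitney test; alpha 0.05; power 80%; equal allocation; attrition 20%; 62 evaluable and 74 recruited per surgery type.

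**Step 1: reproduce the 62.** The two-sample noncentral t calculation is used, with the sample size scaled by the asymptotic relative efficiency (ARE) of the Mann-Whitney test for normal data, 3/π = 0.955. With n per arm:

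- noncentrality = d × √(n × ARE / 2)
- degrees of freedom = 2 × n × ARE − 2

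At n = 31 the noncentrality is 0.75 × √(31 × 0.955 / 2) = 2.885 with 57.2 degrees of freedom, and power is 81.0%. At n = 30 power is 79.6%. So 31 per arm, 62 in total, is the smallest equal-arm size that reaches 80%. The plan's 62 reproduces exactly and has no slack.

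**Step 2: reproduce the 74.**

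- 62 × 1.2 = 74.4, which gives 74 when rounded down (per arm, 31 × 1.2 = 37.2, so 37)
- 62 / (1 − 0.20) = 77.5, which gives 78 when rounded up (39 per arm)

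Only the multiplication returns the stated figure.

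**Step 3: what 74 delivers.**

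- Evaluable after 20% loss: 74 × 0.8 = 59.2, against 62 required
- Attrition that 74 can absorb: 1 − 62/74 = 16.2%
- Check of the alternative: 78 × 0.8 = 62.4, which meets 62

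**Step 4: power within one surgery type at d = 0.75.**

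| Evaluable (per arm) | Power, analytic | Power, simulated |
|---|---|---|
| 62 (31 v 31) | 81.0% | 81.0% |
| 60 (30 v 30) | 79.6% | not run |
| 59 (29 v 30) | 78.9% | 78.3% |

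The simulation used 20,000 replicates with normal data.

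**Step 5: overall figures.** 2 × 78 = 156 against 148, a difference of 8. Evaluable overall: 148 × 0.8 = 118.4, against 2 × 62 = 124. For the one-cohort comparison, 59 per arm gives about 98% power at d = 0.75.

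**The case against.** The strongest reply concerns consequence, since the arithmetic itself is not in dispute.

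1. **The main comparison is safe.** The primary objective compares the two bandages, and section 6.1 has the data analysed as one cohort as well as by surgery type. With about 118 evaluable, that analysis is far above 62. This stands: the shortfall affects only the surgery-specific analyses.

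2. **Loss by day 5 may be well under 20%.** The 20% is argued from follow-up to 12 weeks, and the primary endpoint is at day 5. Table 1 of the protocol, from the earlier osteotomy trial, shows 36 patients at days 5 and 12 and 33 at six weeks, so 3 of 36 (8%) missing by then. At that rate 74 × 33/36 ≈ 68 would remain. This is a fair reason not to expect practical harm, but it does not rescue the stated figure. Table 1 may count analysed rather than randomised patients. Section 6.3 also removes all earlier data of a patient who withdraws, so a late withdrawal would delete a day-5 score, while section 5.3 says such data are kept. The plan itself chose 20%.

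3. **The method of inflation is inferred.** The protocol states no formula, so multiplication by 1.2 is a deduction from the match. That is so. The conclusion does not depend on it, because 74 less 20% is below 62 however 74 was obtained.

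4. **Two power points are less than the uncertainty in the SD.** That is reasonable as a matter of scale, and is why this is a correction to a statement and not a challenge to the design.

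**Conclusion.** The error is real and certain. On the plan's own inputs, 74 per surgery type, 20% attrition and 80% power cannot all hold. The shortfall is 4 patients per surgery type and 8 overall (148 against 156), and power within a type is about 79% instead of at least 80%. The 62 is correct; only the inflation step fails.

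The power figures assume an SD of 2, normally distributed scores for the Mann-Whitney efficiency, near-equal arms, and the full 20% missing from the day-5 analysis. If fewer than about 16% are missing at day 5, 74 is sufficient. The one-cohort comparison is unaffected.

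**What to change.** Correct Table 4 and the matching lines of the protocol summary in one of these ways:

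- keep 74 per surgery type (148 overall) and state that it allows for about 16% attrition; or
- keep 74 and 20%, and state that this leaves 59 evaluable per surgery type, with about 79% power at an SD of 2.

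Either is a change of wording, needs no further patients and costs nothing. If the sponsor wants 20% covered at the stated power, the figures become 78 per surgery type (39 per arm) and 156 overall, which means recruiting 8 more patients and updating the lay summary's 148 and 74 as well. In every case, state the inflation formula, evaluable number divided by (1 − attrition), so that readers can check it.
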